17.1.3. SERIOUS ADVERSE EVENTS

Serious adverse events (SAEs) are those events recorded as "Serious" on the Adverse Events page of the eCRF. A summary of serious TEAEs by SOC and PT will be prepared. A listing will provide details of SAEs and indicate any drug relationship.

17.1.4. ADVERSE EVENTS LEADING TO DEATH

TEAEs leading to Death are those events which are recorded as "Fatal" on the Adverse Events page of the eCRF. These events will be listed.

17.1.5. ADVERSE EVENTS OF SPECIAL INTEREST

17.1.5.1. TEAEs relating to Extrapyramidal Symptoms

The overall incidence of TEAEs relating to Extrapyramidal symptoms (EPS) will be summarized by Preferred Term and treatment group. These will be identified by using a list of specified terms from medical personnel, which can be found in Appendix 3. This summary will be repeated for all Japanese subjects up to Week 52 separately as well.

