3.4.2 Safety variables

- Incidence of adverse events (AEs) and adverse drug reactions (ADRs)
- Incidence of extrapyramidal AEs and ADRs
- Proportion of patients with concomitant use of antiparkinson medication

- Change from baseline in the prior study (D1002001) and the present study (D1002002) in the Drug-Induced Extrapyramidal Symptoms Scale (DIEPSS) total score (except for the overall severity score) at the final assessment and at each assessment point
- Change from baseline in the prior study and the present study in the individual DIEPSS symptoms scores at the final assessment and at each assessment
- Change from baseline in the prior study and the present study in the serum prolactin concentration at the final assessment and at each assessment point
- Change from baseline in the prior study and the present study in the ECG parameter (QTc) at the final measurement
- Change from baseline in the prior study and the present study in the fasting blood glucose, HbA1c (NGSP), glycoalbumin, total cholesterol, LDL cholesterol, HDL cholesterol and triglycerides at the final measurement
- Change from baseline in the prior study and the present study in the body weight at the final measurement
- Laboratory measures and vital signs
- Proportion of patients with any instance of suicide attempt or suicidal ideation based on the Columbia Suicide Severity Rating Scale (C-SSRS)

Rationale

Extrapyramidal symptoms are the most common side effects associated with antipsychotics and usually treated with antiparkinson drugs. The DIEPSS²²⁾ is an evaluation scale for the extrapyramidal symptoms that are caused by drugs.

Antipsychotics are known to increase serum prolactin concentration²³⁾. Some atypical antipsychotics are known to influence glucose metabolism, lipid metabolism, and body weight. Some drugs affect cardiac rhythm (eg, QT interval prolongation).

The rate of suicide is high for bipolar disorder, and prevention of suicide is one of the important aspects in the treatment of bipolar disorder. The C-SSRS²⁴⁾ is a tool designed to systematically assess and track suicidal adverse events (suicidal attempts and suicidal ideation), and is able to comprehensively identify suicidal events while limiting the over-identification of suicidal behavior.

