- For patients who completed the prior study and who received antiparkinson drugs or other drugs for extrapyramidal symptoms at the initiation of the study treatment, the drugs will be continued without any dosage modification.
- For patients who did not participate in the prior study and who did not receive antiparkinson drugs or other drugs for the treatment of extrapyramidal symptoms at screening, drugs for extrapyramidal symptoms will be prohibited from screening until the initiation of the study treatment.
- For patients who did not participate in the prior study and who received antiparkinson drugs or other drugs for the treatment of extrapyramidal symptoms at screening, the drugs should be titrated down appropriately and terminated before the initiation of the study treatment.
- For all patients, if any extrapyramidal symptoms develop or worsen after the initiation of the study treatment, only one of the drugs listed in Table 6 may be used, within the dose range specified in the table. If the drug is not effective, the drug may be replaced by another drug among the drugs listed in Table 6. For akathisia, propranolol (≤ 120 mg/day), amantadine (≤ 300 mg/day), or one of the drugs listed in Table 6 may be used. If the above-mentioned drugs are not available at the study site, similar drugs at equivalent doses may be used with prior authorization of the medical monitor.
- For all patients, antiparkinson drugs and other drugs for extrapyramidal symptoms will be prohibited for prophylactic purposes.

Table 6 Permitted concomitant antiparkinson drugs

Drug	Daily total dose
Biperiden	≤ 16 mg
Trihexyphenidyl	≤ 10 mg
Benztropine	≤ 6 mg
Diphenhydramine	≤ 300 mg

(4) Anxiolytics

From the initiation of the study treatment to the end of the study treatment, only lorazepam (≤ 2 mg/day) can be used as needed for treatment of anxiety, agitation, irritation, and otherwise, but administration will be prohibited within 8 hours before assessment of the MADRS, CGI-BP-S, SDS, HAM-A, YMRS and C-SSRS. If lorazepam is not available at the study site, similar drugs at equivalent doses may be used with prior authorization of the medical monitor. If lorazepam is not effective, another anxiolytics may be used with prior authorization of the medical monitor.

(5) Hypnotics

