6.3 Safety measurements

6.3.1 Adverse events

6.3.1.1 Definitions

The definitions of adverse events (AEs) and serious adverse events (SAEs) are shown below. It is of the utmost importance that all staff members involved in the study are familiar with the content of this section. The principal investigator will be responsible for ensuring that all site staff have read and understand this content.

Adverse events

An adverse event (AE) is any untoward medical occurrence in a patient treated with a medicinal (investigational) product and which does not necessarily have a causal relationship with this treatment. An AE can, therefore, be any unfavorable and unintended sign (eg, an abnormal laboratory finding), symptom, or disease occurring after the administration of a medicinal (investigational) product, whether or not considered related to the medicinal (investigational) product. AEs may include the onset of new illness and the exacerbation of pre-existing conditions.

Lack of efficacy may be an expected potential outcome and should not be reported as an adverse event unless the event is unusual in some way.

The investigator should attempt to establish a diagnosis of the event based on signs, symptoms, and/or other clinical information. In such cases, the diagnosis should be documented as the AE and not the individual signs/symptoms.

Serious adverse events (SAEs)

A serious adverse event (SAE) is an AE that meets one or more of the following criteria:

- Results in death.
- Is life-threatening (ie, a patient is at immediate risk of death at the time of the event, not an event where occurrence in a more severe form might have caused death).
- Requires hospitalization or prolongation of existing hospitalization.
- Results in persistent or significant disability or incapacity.
- Is a congenital anomaly or birth defect.
- Is an important medical event that may jeopardize the patient or may require a medical or surgical intervention to prevent one of the outcomes listed above. Examples of such medical events include allergic bronchospasm requiring

intensive treatment in an emergency room or at home, blood dyscrasias or convulsions that do not result in inpatient hospitalization.

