9.6 Safety analysis

9.6.1 Adverse events

The number and percentage of patients with at least one AE or ADR for each preferred term and system organ class will be summarized for all patients and by treatment group in the prior study. This summary will be repeated for deaths, SAEs, AEs leading to study discontinuation, AEs by severity, extrapyramidal AEs, and AEs by occurrence timing. An ADR will be defined as an AE related to the study treatment, an AE of which causality with study drug is related, probably related or possibly related.

The summary of AEs will be limited to treatment-emergent AEs (TEAEs), and two kinds of TEAEs will be defined as follows:

- TEAEs (up to 28 weeks): AEs with onset on or after Day 1 through 28 weeks
- TEAEs (up to 52 weeks): AEs with onset on or after Day 1 through 52 weeks

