3.6. CHANGES TO ANALYSIS FROM PROTOCOL

The only changes from the planned analysis stated in the protocol (V1.04, Dated 15MAR2016) are related to the subgroup analysis.

- Subgroups to consider: In section 9.5.3 of the protocol, the categories stated for the analysis by mood stabilizer are Lithium, VPA or None. Another category for "Both" (Lithium and VPA) is needed, according to the data collected.
- Efficacy subgroup analysis: Section 9.5.3 in the protocol states that "Subgroup analysis will be conducted for the change from DB and LT baselines in efficacy variables, such as the MADRS total score, the YMRS total score, the CGI-BP-S score (overall, depression, mania) and the HAM-A total score, as well as for the time to recurrence/relapse and time to all cause discontinuation, whenever appropriate.". Subgroup analysis have been included for the above variables with the only exception of the Hamilton Rating Scale for Anxiety (HAM-A).
- Safety subgroup analysis: In addition to the analysis stated in section 9.6.6 of the protocol for the safety variables, mood stabilizer and most recent or current episode subgroup analysis have also been conducted for the Columbia Suicide Severity Rating Scale (C-SSRS).

As per additional request, not initially contemplated in the protocol, a set of summaries containing disposition, demographic and baseline characteristics, exposure and compliance, efficacy and safety data will be added for Japanese subjects by most recent or current episode subgroup, splitting by presence or absence of a Major depressive episode. The details of these summaries are included in section 18 of the current document.

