17.7. OTHER SAFETY ASSESSMENTS

17.7.1. DRUG-INDUCED EXTRAPYRAMIDAL SYMPTOM SCALE (DIEPSS)

The DIEPSS is a clinician-rated assessment of extrapyramidal symptoms induced by antipsychotics and consists of eight individual parameters; gait, bradykinesia, sialorrhea, muscle rigidity, tremor, akathisia, dystonia and dyskinesia; and one global assessment; overall severity. The severity of each item is graded 0 (normal) to 4 (severe), and then a summation of all questions (excluding overall severity) provides the total score, ranging from 0 to 32, which is used for analysis. The investigator will assess the DIEPSS at Week 1 to Week 28 and Week 52 (subjects within Japan) and at discontinuation. The assessment at Week 28, Week 52 or at discontinuation should be performed within 72 hours after the final administration of the study and before the initiation of post treatment with antipsychotics.

A Week 28 (LOCF) endpoint and Week 52 (LOCF) for subjects within Japan will also be derived for DIEPSS. For calculation details, please see section 6.3.

Document: K:\DSP\SM-13496\RVA97109\Biostatistics\Documentation\SAP
 Author: [REDACTED] Version Number: 1.0
 Version Date: 20MAR2018

Template No: CS_TP_BS016 – Revision 3 Reference: CS_WI_BS005
 Effective Date: 01May2012

Copyright © 2012 [REDACTED] All rights reserved.
 The contents of this document are confidential and proprietary to [REDACTED]. Unauthorized use, disclosure or reproduction is strictly prohibited.

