APPENDIX 3. MEDICAL REVIEW OF TERMS

EPS Terms	Metabolic Terms	Combined Terms	Treatment Emergent Mania Terms	Mood Event Terms
Muscle rigidity	Blood cholesterol increased	Parkinsonism: Muscle rigidity, Bradykinesia, Parkinsonism, Tremor, Psychomotor retardation	Bipolar disorder	Disease progression
Trismus	Blood glucose increased		Euphoric mood	Apathy
Bradykinesia	Blood insulin increased		Hypomania	Bipolar disorder
Dystonia	Blood triglycerides increased		Mania	Depression
Parkinsonism	Fructosamine increased			Euphoric mood
Tremor	Glucose urine present			Hypomania
Psychomotor retardation	High density lipoprotein decreased	Dystonia: Dystonia, Trismus		Intentional self-injury
	Lipids abnormal	Somnolence: Hypersomnia, Sedation, Somnolence		Listless
	Low density lipoprotein increased			Mania
	Weight increased			Self-injurious ideation
	Diabetes mellitus			Suicidal ideation
	Dyslipidaemia			Suicide attempt
	Glucose tolerance impaired			
	Hypercholesterolaemia			
	Hyperglycaemia			
	Hyperinsulinaemia			
	Hyperlipidaemia			
	Hypertriglyceridaemia			
	Metabolic disorder			

Document: K:\DSP\SM-13496\RVA97109\Biostatistics\Documentation\SAP
 Author: [Redacted] Version Number: 1.0
 Version Date: 20MAR2018

Template No: CS_TP_BS016 – Revision 3 Reference: CS_WI_BS005
 Effective Date: 01May2012

Copyright © 2012 [Redacted] All rights reserved.
 The contents of this document are confidential and proprietary to [Redacted]. Unauthorized use, disclosure or reproduction is strictly prohibited.

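### The SAP's term list for extrapyramidal adverse events omits akathisia and dyskinesia, so the named EPS incidence can be understated

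*SAP*

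**What the plan says.** Protocol section 3.4.2 names "Incidence of extrapyramidal AEs and ADRs" as a safety variable, and SAP section 2.2 carries the same item as a safety objective. Protocol section 9.6.1 sets out the adverse event summary by preferred term and system organ class and then adds: "This summary will be repeated for deaths, SAEs, AEs leading to study discontinuation, AEs by severity, extrapyramidal AEs, and AEs by occurrence timing". It does not define or restrict the extrapyramidal category.

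SAP section 17.1.5.1 puts this into practice. Overall EPS incidence is summarized by preferred term and treatment group, and repeated for Japanese subjects up to Week 52. On which events qualify, it says: "These will be identified by using a list of specified terms from medical personnel, which can be found in Appendix 3". It gives no standardized query, investigator flag or other route.

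The EPS column of Appendix 3 holds seven terms: muscle rigidity, trismus, bradykinesia, dystonia, parkinsonism, tremor and psychomotor retardation.

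SAP section 3.6 describes the departures from the protocol: "The only changes from the planned analysis stated in the protocol (V1.04, Dated 15MAR2016) are related to the subgroup analysis".

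**The concern.** Akathisia and dyskinesia appear in no column of Appendix 3, yet both documents treat them as extrapyramidal elsewhere. SAP section 17.7.1 describes the DIEPSS as a rating of antipsychotic-induced extrapyramidal symptoms and lists its individual items as "gait, bradykinesia, sialorrhea, muscle rigidity, tremor, akathisia, dystonia and dyskinesia". Protocol section 5.3.2.1 (3), on medication for extrapyramidal symptoms, has its own provision beginning "For akathisia, propranolol".

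Applied as written, the rule leaves out of the EPS incidence any subject whose only extrapyramidal event is coded to akathisia or dyskinesia. Named safety results can then disagree. Such a subject, if given a permitted antiparkinson drug for akathisia, counts in the antiparkinson-use summary and can score on the DIEPSS, but is absent from the EPS adverse event line. Protocol section 3.4.2 itself calls extrapyramidal symptoms the most common side effects of antipsychotics, so readers will look to this line.

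**Working it through.** The plan states no figure to reproduce. The check compares lists and then illustrates the possible size.

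**Step 1: match the DIEPSS items (SAP 17.7.1) to the EPS terms (SAP Appendix 3).**

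| DIEPSS item | EPS term in Appendix 3 |
|---|---|
| Bradykinesia | Bradykinesia |
| Muscle rigidity | Muscle rigidity |
| Tremor | Tremor |
| Dystonia | Dystonia |
| Akathisia | None |
| Dyskinesia | None |
| Gait | Uncertain |
| Sialorrhea | Uncertain |

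Four of the 8 items are covered, 2 have no term (2/8 = 25%) and 2 are uncertain. Gait and sialorrhea are uncertain because protocol section 6.3.1.1 wants the diagnosis "documented as the AE and not the individual signs/symptoms", so these signs may be recorded under the listed term parkinsonism. No listed term offers the same home for akathisia or dyskinesia.

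**Step 2: check whether a row was lost when the table was read.** The Combined Terms column of Appendix 3 has one group reading "Parkinsonism: Muscle rigidity, Bradykinesia, Parkinsonism, Tremor, Psychomotor retardation" (5 terms) and a dystonia group of dystonia and trismus (2 terms). Together, 5 + 2 = 7, and these are the same seven terms as in the EPS column. This agrees with a complete list but does not prove it, because a stand-alone term would not need a combined group. Nothing in the column suggests a missing row.

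**Step 3: direction.** The incidence counts subjects with at least one listed event. Adding terms can only keep or raise that count, so leaving these two out can only keep or lower it.

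**Step 4: whether other tables restore the number.** Let *e* be the subjects with a listed EPS term, *a* those with akathisia and *d* those with dyskinesia, among *N* subjects. The preferred-term tables give *a* and *d* separately. The number with at least one of the three lies anywhere between max(*e*, *a*, *d*) and min(*N*, *e* + *a* + *d*), depending on overlap. The summary tables cannot fix it.

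**Step 5: size.** The shortfall is *N* × *r*, where *r* is the share of subjects whose only EPS event is unlisted. Planned enrolment (protocol 3.5, SAP 3.2) is 325 + 80 = 405, used here because the size of the safety population is not given. The values of *r* are assumptions.

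| Assumed *r* | Subjects missed | Fall in overall EPS incidence |
|---|---|---|
| 0% | 405 × 0 = 0 | 0 points |
| 1% | 405 × 0.01 = 4.05, about 4 | 1 point |
| 3% | 405 × 0.03 = 12.15, about 12 | 3 points |
| 5% | 405 × 0.05 = 20.25, about 20 | 5 points |

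One missed subject is worth 1/405 = 0.25 percentage points overall and 1/80 = 1.25 points in the planned new-recruit group.

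**The case against.** Four points can be made for the plan.

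- **The category is undefined.** The protocol never says what an extrapyramidal adverse event is and leaves detail to the SAP. A term list could be seen as filling that in rather than changing the analysis, and no passage makes the DIEPSS the definition. The list also contains psychomotor retardation, which is not a DIEPSS item. This weakens the charge of an undeclared departure from the protocol. It does not explain why two symptoms that the documents themselves treat as extrapyramidal are outside the list.
- **The list may reflect coded data.** The SAP is dated 20 March 2018, after planned enrolment ended in February 2017, and the appendix is titled as a medical review of terms. If neither event had been reported, nothing would be lost. That is possible, but the SAP describes review of coded terms only for the combined preferred terms (17.1.7.3) and does not say this about the EPS list.
- **The events remain visible.** They appear in the tables by system organ class and preferred term, in the descending-frequency table and in the DIEPSS item scores. The adverse event listings would let someone with access recount subjects. This stands and limits the harm, but the reported incidence would still be the narrow one.
- **No test depends on it.** The study is open-label and has no hypotheses. This bears on severity. The number remains a named safety result.

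**Conclusion.** The concern holds: the EPS rule is wrong as written. It can leave subjects with only akathisia or dyskinesia out of a named safety variable, and for these two terms the error runs in one direction only, downwards.

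The size is unknown and could be zero, since neither document gives a rate for such events. The range of 0 to about 20 of 405 subjects rests on the assumed shares of 0% to 5% and on planned enrolment standing in for the safety population. No claim is made about the net bias of the whole list, because psychomotor retardation could add subjects. Gait and sialorrhea are not counted as gaps.

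This should be corrected. It does not threaten the study's other results, and the individual events are not hidden.

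**What to change.** Add the preferred terms for akathisia and dyskinesia (including tardive dyskinesia) to the EPS column of Appendix 3, and report EPS incidence both including and excluding akathisia so that the narrower figure stays available. The same list should drive the Week 28 summary and the Japanese Week 52 repeat. Terms for gait and salivation can be considered at the medical review of coded terms before database lock.

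If the exclusion is deliberate, state it in SAP section 3.6 with the reason, as protocol section 9.1 requires for changes to the planned analysis. If the list was limited to terms already found in the coded data, one sentence saying so would settle the matter.

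The cost is a term-list edit and one more table line. With no hypotheses to test, there is no multiplicity consequence. The EPS incidence may become less favourable.

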17.1.5.2. Metabolic TEAEs

The overall incidence of Metabolic TEAEs will be summarized by Preferred Term and treatment group. These will be identified by using a list of specified terms from medical personnel, which can be found in Appendix 3. This summary will be repeated for all Japanese subjects up to Week 52 separately as well.

17.1.5.3. Mood event-related TEAEs

The overall incidence of mood event-related TEAEs will be summarized by Preferred Term and treatment group. These will be identified by using a list of specified terms from medical personnel, which can be found in Appendix 3. This summary will be repeated for all Japanese subjects up to Week 52 overall, by Mood Stabilizer and by Most Recent or Current Episode subgroups separately as well.

Document: K:\DSP\SM-13496\RVA97109\Biostatistics\Documentation\SAP

Author: [REDACTED]

Version Number:

1.0

Version Date:

20MAR2018

Template No: CS_TP_BS016 – Revision 3

Reference: CS_WI_BS005

Effective Date: 01May2012

Copyright © 2012 [REDACTED] All rights reserved.

The contents of this document are confidential and proprietary to [REDACTED]. Unauthorized use, disclosure or reproduction is strictly prohibited.

17.1.6. SUBGROUP ANALYSIS OF ADVERSE EVENTS

An overall summary of adverse events will be presented for all subjects up to Week 28 overall and by country, and repeated for all Japanese subjects up to Week 52 overall, by Sex, Age, Mood Stabilizer and Most Recent or Current Episode subgroups separately as well.

Other adverse event summaries will be repeated for all Japanese subjects up to Week 52 separately as noted in the appropriate sections.

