9.5.3 Subgroup analysis

Subgroup analysis will be conducted for the change from DB and LT baselines in efficacy variables, such as the MADRS total score, the YMRS total score, the CGI-BP-S score (overall, depression, mania) and the HAM-A total score, as well as for the time to recurrence/relapse and time to all cause discontinuation, whenever appropriate. Subgroups will include country, sex, age, mood stabilizer (lithium, VPA, or none), most recent or current episode (major depressive, manic, hypomanic, or mixed episode), bipolar I diagnosis subtype (rapid cycling or non-rapid cycling) and psychotic features (with or without). Selected subgroup analyses will be repeated for patients enrolled in Japan. Details of subgroup analysis will be provided in the statistical analysis plan.

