9.6.6 Subgroup analysis

Subgroup analysis will be conducted in AE summaries and changes from DB and LT baselines in the DIEPSS total score, serum prolactin concentration, fasting blood glucose, HbA1c (NGSP), glycoalbumin, total cholesterol, LDL cholesterol, HDL

cholesterol, triglycerides, body weight, and ECG parameter (QTc). Subgroups will include country, sex, age and mood stabilizer, most recent or current episode. Selected subgroup analyses will be repeated for patients enrolled in Japan. Details of subgroup analysis will be provided in the statistical analysis plan.

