16.1.4. ANALYSIS OF EFFICACY VARIABLE(S)

16.1.4.1. Analysis of MADRS, YMRS, CGI-BP-S, SDS and HAM-A

Observed and change from DB baseline and LT baseline to each post-baseline visit including Week 28 (LOCF) endpoint and Week 52 (LOCF) endpoint for subject within Japan, will be summarized for the safety population by treatment group for the following scores:

- MADRS total score
- YMRS total score
- CGI-BP-S overall score
- CGI-BP-S depression score
- CGI-BP-S mania score
- SDS total score and subscale scores of work/school, social life or leisure activities, and home life or family responsibilities, and days lost and days underproductive
- HAM-A total score

MADRS total score, YMRS total score and CGI-BP-S overall score summaries will be presented for all subjects up to Week 28 overall, by country (excluding Japan), Sex, Age and Mood Stabilizer subgroups separately, and will be repeated for all Japanese subjects up to Week 52 overall, by Sex, Age, Mood Stabilizer, Most Recent or Current Episode, Bipolar I Subtype and Psychotic Features subgroups separately as well.

CGI-BP-S depression and mania score summaries will be presented for all subjects up to Week 28 overall and by country (excluding Japan) separately, and will be repeated for all Japanese subjects up to Week 52 overall, by Sex, Age, Mood Stabilizer, Most Recent or Current Episode separately as well.

SDS total score and subscale scores and HAM-A total score summaries will be presented for all subjects up to Week 28 and repeated for all Japanese subjects up to Week 52.

16.1.4.2. Time to recurrence/relapse of any mood event from clinical stability of bipolar I disorder

Time to recurrence/relapse of any mood event from clinical stability of bipolar I disorder will be analyzed using a time-to-event analysis. Kaplan-Meier (KM) results will be displayed for the 25%, 50% and 75% quartiles, including its 95% confidence interval using the product limit method. The KM figure will be produced to support the analysis. The time to recurrence/relapse of any mood event from clinical stability of bipolar I disorder will be presented for all subjects up to Week 28 overall, by country, Sex, Age and Mood Stabilizer separately, and will be repeated for all Japanese subjects up to Week 52 overall, by Sex, Age, Mood Stabilizer, Most Recent or Current Episode, Bipolar I Subtype and Psychotic Features separately as well.

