17.7.1.3. Subgroup Analysis of DIEPSS

Observed, DB baseline and LT baseline and change from DB baseline and LT baseline at Weeks 28 and 28 (LOCF) analyses will be repeated for all subjects up to Week 28 overall and by country (excluding Japan) and separately at Weeks 52 and 52 (LOCF) for Japanese subjects up to Week 52 overall, by Sex, Age and Mood Stabilizer, only for DIEPSS total score (excluding overall severity).

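### The SAP limits the sex, age and mood-stabilizer breakdowns of AEs, weight, DIEPSS and (in its operative sentence) QTc to Japanese subjects, and SAP 3.6 does not list this as a change

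*SAP*

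**What the plan says.** **Protocol.** Section 9.6.6 states that "Subgroup analysis will be conducted in AE summaries and changes from DB and LT baselines in the DIEPSS total score", and goes on to name prolactin, the glucose and lipid measures, body weight and QTc. It then fixes the factors: "Subgroups will include country, sex, age and mood stabilizer, most recent or current episode". Japan comes in afterwards, as a repeat of selected analyses. Section 9.5.3 is built the same way for efficacy, with bipolar subtype and psychotic features as further factors. Section 9.1 requires any change from the protocol's analysis to be listed in the SAP with its reason.

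**SAP, safety.** For AEs, 17.1.6 says "An overall summary of adverse events will be presented for all subjects up to Week 28 overall and by country"; sex, age, mood stabilizer and episode follow only for Japanese subjects to Week 52. For DIEPSS total, 17.7.1.3 says the tables "will be repeated for all subjects up to Week 28 overall and by country (excluding Japan"), with sex, age and mood stabilizer again only for Japan. Weight/BMI (17.5.3) follows this pattern. QTc (17.4.4) opens by promising all the section 7.5 subgroups, and then specifies the same Japan-only split. The selected labs (17.3.3) open with the same promise, and then specify sex for all subjects but age and mood stabilizer for Japan only.

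**SAP, efficacy.** For MADRS, YMRS and CGI-BP-S overall, 16.1.4.1 says summaries "will be presented for all subjects up to Week 28 overall, by country (excluding Japan), Sex, Age and Mood Stabilizer subgroups separately". Relapse and discontinuation (16.1.4.2, 16.1.4.3) are treated alike.

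**SAP, declaration.** Section 3.6 says the changes it lists are the only ones. On efficacy it says: "Subgroup analysis have been included for the above variables with the only exception of the Hamilton Rating Scale for Anxiety (HAM-A"). On safety it lists only an addition, for the C-SSRS.

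**The concern.** Safety is half of the study objective. As the tables are specified, a non-Japanese subject contributes to no sex, age or mood-stabilizer breakdown of AEs, weight or DIEPSS and, on the operative sentence, none of QTc. For DIEPSS, weight/BMI and QTc, the Japanese subgroup tables are set at Weeks 52 and 52 (LOCF) and the all-subject tables at Weeks 28 and 28 (LOCF). So no Week 28 subgroup table by these factors is specified for these variables even within Japan.

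Restricting mood stabilizer to Japan also mixes that factor with cohort. Lithium or VPA is mandatory for the new recruits, who enter with a manic, hypomanic or mixed episode, and optional for completers, who enter with depression. The group taking neither drug in Japan should therefore be almost entirely completers. Completers outside Japan may also take either drug, so including them would add a contrast within one cohort.

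Finally, a reader who relies on SAP 3.6 would believe that the protocol's safety subgroups were run as written.

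**Working it through.** No power or alpha figure is involved, because the study tests no hypothesis. The check sets each protocol-named combination of variable and factor against the SAP section that specifies it.

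| Variables | SAP | All subjects, Week 28 | Japanese subjects only |
|---|---|---|---|
| AE overview (1) | 17.1.6 | country | sex, age, mood stabilizer, episode |
| DIEPSS total, weight, QTc (3) | 17.7.1.3, 17.5.3, 17.4.4 | country | sex, age, mood stabilizer |
| Prolactin, glucose, HbA1c, glycoalbumin, total, LDL and HDL cholesterol, triglycerides (8) | 17.3.3 | country, sex | age, mood stabilizer |
| MADRS, YMRS, CGI-BP-S overall, relapse, discontinuation (5) | 16.1.4.1 to 16.1.4.3 | country, sex, age, mood stabilizer | episode, subtype, psychotic features |
| CGI-BP-S depression, mania (2) | 16.1.4.1 | country | sex, age, mood stabilizer, episode |
| HAM-A (1) | 3.6 | none (declared) | none |

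**Safety by sex, age and mood stabilizer.** Specified: 12 variables × 3 factors = 36.
- Japan-only: AEs, DIEPSS, weight and QTc give 4 × 3 = 12, and labs by age and mood stabilizer give 8 × 2 = 16. The total is 28 of 36 (78%).
- All subjects: labs by sex, 8 of 36.
- Strength of the reading: in 17.3.3 and 17.4.4 the opening sentence conflicts with the operative one. This touches 16 lab and 3 QTc combinations, 19 of the 28. The remaining 9 (AEs, DIEPSS and weight, 3 × 3) have no conflicting sentence in their own sections.

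**All safety factors.** Specified: 12 × 5 = 60.
- All subjects: 12 (country) + 8 (labs by sex) = 20.
- Japan-only: 28 + 1 (AEs by episode) = 29.
- Not run: episode for the other 11 variables = 11.

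**Efficacy.** Specified: 8 × 7 = 56.
- All subjects: 5 × 4 + 2 × 1 = 22.
- Japan-only: 5 × 3 + 2 × 4 = 23.
- Not run: HAM-A 7, plus subtype and psychotic features for CGI-BP-S depression and mania 2 × 2 = 4, making 11.

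**Both together.** Specified 60 + 56 = 116: all subjects 42, Japan-only 52, not run 22. Japan-only is 52/116 = 45% of those specified, and 52/94 = 55% of those run.

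**Declaration.** SAP 3.6 lists an added category for taking both mood stabilizers, the HAM-A omission, the C-SSRS addition and extra Japanese summaries by episode. None of the 52 Japan-only restrictions is listed. Of the 22 combinations not run, only the 7 for HAM-A are.

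**Subjects affected.** Planned enrolment is 325 + 80 = 405. Only the 80 new recruits are known to be Japanese (80/405 = 20%), so at most 325 (80%) are non-Japanese. The documents do not split the completers by country.

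**The case against.** **The protocol left discretion.** Sections 9.5.3 and 9.6.6 both defer details to the SAP, and 9.5.3 limits efficacy subgroups to where they are appropriate. SAP 7.5 likewise leaves the choice of safety subgroups to the individual sections. This stands in part. It weakens any complaint about subtype, psychotic features and CGI-BP-S depression/mania. Section 9.6.6 has no such qualifier for safety, and deferring details does not cancel the 9.1 duty to list changes.

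**Japan is the natural place for some factors.** Restricting episode type loses little, since every non-Japanese subject comes from the bipolar depression study. For mood stabilizer, both drugs were barred in the prior study and are mandatory only for the Japanese new recruits. That is a plausible reason, but the SAP does not give it, and the SAP runs the same factor in all subjects for five efficacy variables. Neither argument reaches sex or age.

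**QTc may be covered.** The opening sentence of 17.4.4 can be read as extending to every subgroup. This stands as far as it goes: QTc is an inconsistency to resolve, not a plain omission. The sex-specific QTc threshold in 17.4.3 is reported for all subjects, but it is not a breakdown by sex.

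**Stronger readings.** A reader might infer that the SAP moves most protocol subgroups to Japan, or turns the protocol's structure round. The tally does not support this: 45% of those specified are Japan-only, and for the five efficacy variables above, the sex, age and mood-stabilizer subgroups keep the protocol's structure. A majority is clear only for the safety subgroups other than country: 29 of 48 (60 − 12).

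**Conclusion.** The point holds in a limited form. For AEs, weight and DIEPSS total, the protocol's sex, age and mood-stabilizer breakdowns are specified in Japanese subjects only. The same is true of the selected labs by age and mood stabilizer, and of QTc, if the operative sentences of 17.3.3 and 17.4.4 govern. That is 28 of 36 combinations, 9 of them free of any conflicting sentence. The efficacy restrictions are real but of less weight. SAP 3.6 is inaccurate on either reading of those two sections, because the AE, weight and DIEPSS restrictions and the efficacy ones are missing from it in any case.

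A reader might also want to express the loss as wider standard errors. The documents do not support a figure: the Japanese share of completers is not stated, and the all-subject and Japanese tables refer to different time points. Since no hypothesis is tested, no inference fails. What is lost is description of safety in non-Japanese subjects, and a true record of changes.

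**What to change.** 1. In SAP 17.1.6, 17.5.3, 17.7.1.3 and 17.4.4, add sex, age and mood stabilizer to the all-subjects Week 28 outputs for AEs, weight/BMI, DIEPSS total and QTc. In 17.3.3 add age and mood stabilizer for the selected labs. Keep the Japanese Week 52 repeats.
2. Reconcile the opening and operative sentences of 17.3.3 and 17.4.4, so that each names the subgroups and populations actually run.
3. In SAP 3.6, list with a reason every restriction or omission that remains: episode type, bipolar subtype, psychotic features and CGI-BP-S depression/mania.

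The cost is repeat runs of existing table programs and a wording change. No new data are needed: sex, age and mood-stabilizer subgroups are already run in all subjects for the main efficacy variables. With no hypotheses, there is no multiplicity cost. If the extra tables are declined, the minimum is to declare the safety restrictions in 3.6 with their reasons. That makes the record accurate but leaves the non-Japanese subjects outside these breakdowns.
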